19.1 Regulatory Oversight

The proposed extension will be reviewed and approved by the IRBs of all the participating institutions in the U.S., Uganda and Kenya. This includes the UCSF Committee on Human Research (CHR), the Makerere University School of Medicine - Research and Ethics Committee (SOMREC), the Uganda National Council of Science and Technology (UNCST), the Kenya Medical Research Institute (KEMRI). As described in Section 18.0, this study will employ four levels of data and participant safety monitoring including Study Steering Committee oversight, US and host country Institutional Review Board (IRB) review, Data Safety Monitoring Board (DSMB) Review, and External Clinical Site Monitoring. **Table 9** describes event reporting guidelines to individual IRBs overseeing this study.

CAB-LA was very well tolerated in the registration studies. For this extension, SAEs will be captured in the intervention arm and Grade 3 and 4 AEs and non-serious ADRs leading to withdrawal will be captured for participants on CAB-LA. Grade 3 and 4 AEs will be graded and recorded using the NIAID Adverse Event Grading of Severity scale (<https://rsc.niaid.nih.gov/clinical-research-sites/daids-adverse-event-grading-tables>). Clinical Adverse Events not identified elsewhere are described in **Table 10**. The Clinical Management Team (CMT) will be notified of SAEs as soon as possible and will be reported per regulatory guidelines as stated in **Table 9** below.

Table 9. Reporting Guidelines

Institution	Contact information	Type of Event	Reporting Timeframe	Reporting Method
UCSF IRB	UCSF Committee for Human Research [name] [contact]	SAEs/ Grade 3 or higher AEs that change the study risks or benefits, OR necessitates modification to the IRB-approved consent document(s), and/or the IRB-approved application/protocol	Within 10-working days of awareness	Via online reporting system
NIAID	[name], Program Officer, NIH	SAEs or Harm determined to be possibly, probably or definitely related to study intervention Participants administered CAB-LA: All pregnancies	At the time of reporting to IRBs One-week of awareness (Pregnancies)	Email

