19.5 Adverse Event Procedures and Reporting Requirements

For persons receiving CAB-LA, Grade 3 and 4 AEs will be monitored in addition to SAEs.

Grade 3

Any grade 3 or higher clinical or laboratory AE observed prior to their first injection of active CAB will prompt consultation with the clinical officer (CO) prior to any injectable dosing.

At any time, participants who develop a Grade 3 AE or toxicity that is not specifically addressed in the Table below and is judged to be related to CAB-LA by the Investigator, CAB-LA use will be temporarily discontinued. In general, the investigator will re-evaluate the participant until resolution of the toxicity. For Grade 3 AEs deemed related to CAB-LA, will be permanently discontinued if improvement to severity \leq Grade 2 cannot be documented within 4 weeks of awareness. If CAB-LA is resumed after holding for a Grade 3 AE and the same Grade 3 AE recurs without alternative explanation, CAB-LA will be permanently discontinued. For Grade 3 AEs deemed unrelated to CAB-LA, the participant may continue with appropriate clinical management by the site, per local standards of care.

Grade 4

Any grade 4 or higher clinical or laboratory AE observed prior to first injection will prompt evaluation and may requiring holding of dosage, as determined by the CO and CMT. Participants who develop a Grade 4 AE or toxicity that is not specifically addressed in **Table 11** (regardless of relationship to CAB-LA) will have the CAB-LA injections temporarily discontinued. CAB-LA use will not be resumed if the Grade 4 AE is considered by the Investigator to be related to the injections. If CAB-LA use is resumed and the same Grade 4 AE recurs at Grade 4 level at any time, CAB-LA will be permanently discontinued, unless an alternative explanation for the recurrence is clearly documented.

Pregnancy

Any pregnancy that occurs during in participants taking CAB-LA must be reported using the Pregnancy Reporting Case Report form to NIAID and ViiV Healthcare within **one week** of learning of its occurrence. Pregnancies that are associated with SAEs will be reported within 72 hours using the Adverse Event CRF, Country-specific SAE Reporting form, and supplemental information attached.

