Our secondary objective to evaluate implementation will follow the RE-AIM framework and corresponding measures (defined in Table 4). Analyses assessing the primary measures of Reach, Adoption, Implementation and Maintenance will be based on standard descriptive statistics. Analyses to evaluate Effectiveness will compare covered time over the 48 week CAB-LA extension period to covered time prior to the CAB-LA extension among intervention participants. We will adjust for measured changes in participant characteristics between these two follow-up periods, using a TMLE designed for serial measures. Measures of control participants will also be used to adjust for temporal trends. We will test the null hypothesis that coverage of the DCP model with CAB-LA is the same as coverage of the DCP model without CAB-LA. We will again use a two-sided test at the 5% significance level. Primary analyses will again pool over trials, while secondary analyses will be stratified by trial. In addition, we will evaluate marginal and adjusted predictors of CAB-LA uptake and persistence. Our tertiary objective to evaluate changes in knowledge, awareness, and acceptability/satisfaction will be based on applying TMLE to survey data, accounting for repeated measures.

Additional descriptive analyses will include HIV incidence and safety. HIV seroconversions will be measured in each arm and incidence rates will be calculated using person time at risk. Safety Grade 3 and Higher AEs and SAEs will be measured for participants using CAB-LA and incidence rates will be calculated during person time exposed. These analyses will be complemented with costing evaluations as well as participant and provider qualitative data from IDI.

All analyses of the community-based trial will account for clustering.

21.2 Pharmacokinetic analyses:

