5. ADDITIONAL DESCRIPTIVE ANALYSES

We will summarize participant follow-up, overall and by arm. Follow-up in the CAB-LA extension study starts at enrollment and ends at the earliest of HIV diagnosis, death, withdrawal, or December 31, 2023. Follow-up time is censored during periods without data on use of biomedical HIV prevention.

Overall and by arm, we will report the number and proportion of participants who withdrew, died, or had other adverse events. We may also report on outcomes among women who become pregnant after initiating CAB-LA. We will summarize data on biomedical HIV prevention product use by arm. These summaries will exclude participants without any follow-up data on biomedical prevention use. We will use heatmaps to depict participant-level use of prevention products over months of follow-up in the extension. We will also provide descriptive statistics about product use over time, including the month prior to the extension study, at baseline in the extension study, and ever use during the extension study. When calculating these descriptive statistics, missing values at baseline product use will be imputed from the first follow-up month.

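### SAP Section 5 tabulates adverse events by arm, but non-fatal events are not systematically ascertained in the control arm, so the by-arm and overall figures are not interpretable

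*SAP*

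**What the plan says.** SAP Section 5, headed "ADDITIONAL DESCRIPTIVE ANALYSES", sets the reporting rule: "Overall and by arm, we will report the number and proportion of participants who withdrew, died, or had other adverse events". It plans no safety test and no effect estimate.

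The protocol sets the collection rules, and they depend on arm and on product:

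- Section 19.1 on serious events: "SAEs will be captured in the intervention arm".
- Section 19.1 on other events: "Grade 3 and 4 AEs and non-serious ADRs leading to withdrawal will be captured for participants on CAB-LA".
- Section 19.5: "For persons receiving CAB-LA, Grade 3 and 4 AEs will be monitored in addition to SAEs".
- Tables 5 and 6: the row for adverse event monitoring stands only in Table 6, the schedule for CAB-LA users. Table 5, which covers the standard-of-care arm and intervention participants not on CAB-LA, has no such row.
- Section 8.1: control visits every 24 weeks consist of HIV testing, weight and a survey on prevention use and risk, with drug-level samples from those reporting PrEP or PEP.

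The safety analysis in Protocol 21.1 is not by arm: "Safety Grade 3 and Higher AEs and SAEs will be measured for participants using CAB-LA and incidence rates will be calculated during person time exposed".

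**The concern.** A by-arm proportion is informative only if the event is looked for in the same way in both arms. Here it is not. A reader of the SAP table would see non-fatal events in the intervention arm and few or none in the control arm, and could attribute the gap to the intervention or to CAB-LA. The trial is open-label, and Protocol 22 notes that the product was not yet approved in either country, so a safety table is likely to be read closely.

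Two further faults do not depend on the control arm. Within the intervention arm, CAB-LA users contribute SAEs plus Grade 3 and 4 events, while non-users contribute SAEs only. One proportion over the whole arm therefore has a numerator whose scope changes from person to person. The overall proportion has in its denominator people who were not monitored at all.

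**Working it through.** **Step 1. Who is looked at for what**

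| Event | Control arm | Intervention, not on CAB-LA | Intervention, on CAB-LA |
|---|---|---|---|
| Death, withdrawal | Yes (Protocol 7.3, SAP 5: both end follow-up) | Yes | Yes |
| SAE | No provision stated | Yes (19.1) | Yes (19.1, 19.5) |
| Grade 3 and 4 AE | No provision stated | No provision stated | Yes (19.1, 19.5, Table 6) |
| Non-serious reaction leading to withdrawal | No provision stated | No provision stated | Yes (19.1) |
| Visit interval (8.1) | 24 weeks | 12 weeks | 4 weeks at first, then 8 weeks |

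Only the first row supports a by-arm comparison. The last row shows that spontaneous reports would also be unequal, because contact is more frequent in the intervention arm.

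**Step 2. Form of the distortion**

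The documents give no adverse event rate, expected count or safety power, so there is no stated figure to reproduce. Let p be the true risk, equal in both arms. Let capture be complete in the intervention arm and a fraction c in the control arm, with n per arm. Then:

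- expected intervention count = n × p
- expected control count = n × p × c
- apparent difference = p − p × c = p(1 − c)
- overall proportion = p(1 + c)/2

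Complete capture across the intervention arm fits SAEs. For non-serious Grade 3 and 4 events, only the share u of that arm on CAB-LA is monitored. If the risk in users is r, the arm-wide proportion shows u × r. The documents do not give u or r.

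**Step 3. Illustration**

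n = 485 per arm, from SAP Section 7, is used only for scale. The values of p and c are assumptions. The last three columns give the exact binomial probability that a two-sided Fisher test would fall below 0.05. The plan contains no such test; it serves here only to gauge how convincing the display would look.

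| p | Intervention, n × p | Control, c = 0 | Control, c = 0.25 | Fisher < 0.05, c = 0 | Fisher < 0.05, c = 0.25 | Fisher < 0.05, c = 1 |
|---|---|---|---|---|---|---|
| 1% | 4.85 | 0 | 1.2 | 36% | 16% | 2.1% |
| 2% | 9.7 | 0 | 2.4 | 92% | 46% | 3.1% |
| 3% | 14.55 | 0 | 3.6 | 99.7% | 69% | 3.4% |
| 5% | 24.25 | 0 | 6.1 | about 100% | 92% | 3.6% |

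The apparent difference at p = 2% is 2 points with c = 0 and 0.02 × 0.75 = 1.5 points with c = 0.25. The overall proportion at p = 2% and c = 0 is 9.7/970 = 1%, half the true risk.

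For a small split, 6 versus 0 gives p = 2 × (485 × 484 × 483 × 482 × 481 × 480)/(970 × 969 × 968 × 967 × 966 × 965) = 0.031.

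The true risk is the same in both arms in every row, so all of the apparent difference comes from ascertainment. With equal capture (c = 1) the expected difference is 0.

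**The case against.** The strongest reply is that nothing here amounts to a planned safety comparison. The SAP line is descriptive, reads largely as a disposition summary, and carries no test. Safety is not among the between-arm endpoints in SAP Section 1. Protocol 21.1 already plans the appropriate analysis, and the SAP does not withdraw it. All of this stands. A reader might infer that the plan makes a false safety inference; the documents do not support that. The fault is in a display.

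A reader might also infer that the control-arm count is zero by construction. That goes too far as well:

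- Section 19.1 names the intervention arm for SAEs but does not exclude recording elsewhere.
- Several rows of Table 9 (the Kenyan and Ugandan ethics bodies and the Ugandan drug authority) are not limited by arm, so a control SAE could be reported ad hoc.
- The SAP wording counts death among the adverse events, and deaths are followed in both arms.
- The missing row in Table 5 is weak evidence alone, because SAEs are captured in the whole intervention arm although that table has no such row for non-users.

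The numerical illustration is open to challenge too: the risks and the control capture are assumed, and the result moves a good deal with c.

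What the reply does not remove is the by-arm line itself. A reporting route for events that happen to come to notice is not ascertainment, and no section sets up adverse event assessment for control participants. The analysis in 21.1 would stand beside the by-arm table without correcting it.

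**Conclusion.** The SAP's by-arm rule does not match what the protocol collects. Non-fatal adverse events in the control arm are not systematically ascertained, so their count would be zero or near zero and could not be interpreted. The intervention-arm proportion mixes two levels of capture, and the overall proportion is diluted by unmonitored people. This conclusion rests on the text alone.

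The size cannot be derived from the documents. Under the stated assumptions, an apparent difference of 1 to 5 percentage points would arise with no control capture, and 0.75 to 3.75 points with 25% capture, for true risks of 1% to 5% that are equal in both arms.

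No primary or secondary endpoint and no planned inference is affected. The by-arm figures for deaths and withdrawals in the same sentence are sound. This is a reporting correction that should be made before the table is produced.

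**What to change.** In SAP Section 5:

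1. Limit the overall and by-arm summary to deaths and withdrawals.
2. Report SAEs and Grade 3 or higher events in CAB-LA users as incidence rates per exposed person-time, as in Protocol 21.1. This covers SAEs as well as graded events.
3. If wanted, list SAEs for the whole intervention arm, without a between-arm comparison.
4. Where a table has a control column, mark non-fatal adverse events there as not systematically collected, never as 0. Add a footnote stating who was monitored for what.
5. Reconcile Protocol 19.1, 19.5 and 21.1 with SAP Section 5 so that one statement covers which events are collected, in whom, and with which denominator.

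The cost is wording only. No data collection, sample size or analysis of an endpoint changes. The one loss is that no comparative adverse event table is shown, and the collection rules could not support one.

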6. SENSITIVITY ANALYSES

In this extension study, participants will maintain their original randomization arm. As a result, there is a legitimate concern that arms will be imbalanced at the start of the extension study. We will address this concern by conducting the following sensitivity analyses for the effect on biomedical HIV prevention coverage (primary endpoint) and at-risk coverage (secondary endpoint). These analyses will incorporate data from all persons who participated in the 3 Dynamic Choice HIV Prevention trials – regardless if they continued in the extension and/or had their endpoint ascertained in the extension.

This sensitivity analysis is informed by the Causal Roadmap¹⁶ and aims to address possible bias due to selection and missing data. Specifically, we can frame the analysis as asking, “What is the effect of the SEARCH Dynamic Choice HIV Prevention intervention (including the option of CAB-LA) if all participants had continued in the extension and had their endpoint ascertained?” While the treatment arm is randomized, we need to make the following missing data assumption: within values of adjustment variables, participants with their endpoint measured in the extension (and, thus, continued in the extension) are representative of participants who do not. Here, our adjustment set includes variables measured at recruitment into the initial trials (hereafter “baseline”): age, sex, country, recruitment site, alcohol use, and mobility. Importantly, our adjustment set also includes trial arm as well as post-intervention variables measured prior to the extension start: biomedical HIV prevention coverage, at-risk coverage, follow-up time, and follow-up time with self-reported risk of HIV acquisition. We additionally need that there is a positive probability of endpoint ascertainment within all possible values of these adjustment variables.

Under these assumptions, our statistical estimand is given by the Longitudinal G-computation formula:¹⁷

$$\mathbb{E}\{\mathbb{E}[\mathbb{E}(Y|\Delta = 1, L1, A = 1, L0)|A = 1, L0]\} - \mathbb{E}\{\mathbb{E}[\mathbb{E}(Y|\Delta = 1, L1, A = 0, L0)|A = 0, L0]\}$$

where Y is the endpoint, Δ is an indicator of having that endpoint measured and, thus, continuing in the extension, $L1$ are the time-varying covariates, A is an indicator of being randomized to the intervention arm, and $L0$ are the baseline covariates.

For estimation and inference, we will use longitudinal TMLE as implemented in the `ltmle` package.^{4,14,18} In the main analysis, we will employ Super Learner, which is an ensemble machine learning method, to flexibly adjust and to improve efficiency.¹⁹ Within Super Learner, we will combine predictions from main terms logistic regression (GLM), generalized additive models (GAM), multivariate adaptive splines (MARS), and the mean. The main analysis will also bound the estimated propensity scores (for measurement) from below at 1%. We will use the same approach for statistical inference and multiple testing as the primary analysis.

We will further examine the sensitivity to our assumptions and analytic choices by implementing TMLE as follows:

- TMLE with Super Learner (as described above) but bounding the estimated propensity scores from below at 2%
- TMLE with main terms logistic regressions (instead of Super Learner)
- TMLE with Super Learner but only adjusting for baseline variables
- TMLE with main terms logistic regressions and only adjusting for baseline variables

[figure not shown]
We will implement these analyses for biomedical HIV prevention coverage (primary endpoint) and at-risk coverage, overall and within the predefined subgroups.

7. POWER CALCULATIONS

We assume 70% of participants in the 3 Dynamic Choice HIV Prevention trials enroll in the extension. Of those, we assume 90% have measures of biomedical HIV prevention coverage (the primary endpoint). Then using standard formulas for continuous outcomes with clustering,^{20,21} we anticipate at least 80% power to detect at least a 7.5% absolute increase in prevention coverage with 485 participants/arm, an outcome standard deviation of 0.35, and a design effect of 1.3. As shown in Figure 2, these calculations are fairly robust to alternative assumptions, including lower outcome measurement

and higher design effects. We further expect these calculations to be conservative given the precision gains due to covariate adjustment with TMLE in the primary analysis.

Figure 2: Minimal effect size (difference) detected with 80% power with a two-sample t-test (via `power.t.test` in R) after deflating the sample size by the design effect

8. HISTORY OF CHANGES

Version 1.0: This version includes updated power calculations (as compared to the Study Protocol v7.0) to reflect enrollment into the extension and that the primary analysis pools over and adjusts for (versus stratifies on) recruitment setting.

Version 1.1 (current version): This version includes additional details about the pre-specified sensitivity analyses (Section 5.0).

